3.3 Definition of Withdrawal from Treatment and Study

The group of patients who withdrew from treatment and the scheduled visits in the Treatment Period will be described as *withdrawn from treatment*. The complementary group will be described as *completed treatment*.

Patients who withdraw from treatment due to withdrawal of consent or lost to follow-up will also be described as withdrawn from study. In this case, the reason for withdrawal from study will be set to the same reason as that for withdrawal from treatment.

Patients who attend the Safety Follow-up visit (scheduled six weeks after last dose of IMP), regardless of whether they complete the Treatment period will be described as *completed study*. Patients who do not attend the Safety Follow-up visit will be described as *withdrawn from study*. This definition reflects the “Summary of Study” form in the eCRF.

4 Endpoints

Rules for calculation of derived scores and for assigning data to visits as well as descriptions of the scales used in the study are described in Section 19.

4.1 Primary Endpoints

- Primary safety and tolerability endpoints:
 - Adverse events
 - Absolute values, changes values from baseline and potentially clinically significant values in:
 - Clinical safety laboratory tests
 - Body weight, BMI, and waist circumference
 - Vital signs (systolic blood pressure, diastolic blood pressure, and pulse)
 - ECG parameters (ventricular rate, RR, PR, QRS, QT, and QT_{CF})

4.2 Exploratory Endpoints

- Exploratory safety and tolerability endpoints:
 - Change from baseline in AIMS, BARS Global Clinical Assessment of Akathisia score (item 4) score and mSAS total score
 - C-SSRS
- Exploratory efficacy endpoints:
 - *Psychotic symptoms*
 - Change from baseline in PANSS total score
 - Change from baseline in PANSS subscale scores (PANSS Negative Symptoms subscale, PANSS Positive Symptoms subscale, PANSS General Psychopathology subscale)
 - *Negative symptoms*
 - Change from baseline in NSA-4 total score
 - Change from baseline in PANSS Marder factor score (negative symptoms)
 - *Global clinical impression*
 - Mean change from baseline in CGI-S score
 - *Andreasen symptoms remission*
 - Remission (simultaneous ratings of mild or less on PANSS specific items: P1, G9, P3, P2, G5, N1, N4, and N6) at Week 52 Visit
 - *Quality of life and functioning*
 - Change from baseline in QLS score
 - Change from baseline in ToolL score
 - Change from baseline in WorQ score
 - Change from baseline in PSP total score
 - *Treatment satisfaction*
 - Change from baseline in MSQ score
 - Health care resource used during the 52-week study period

5 Analysis Sets

The patients will be assigned to analysis sets based on IMP intake and post-baseline assessments of the efficacy variable(s) in the Treatment Period.

Due to a higher-than-anticipated roll-over rate and a lower-than-anticipated attrition rate from study 16159A, only patients from study 16159A and 16323A are enrolled in the study, i.e. no patients who have not previously participated in a study investigating Lu AF35700 are enrolled.

Only 4 patients from study 16323A are enrolled. Therefore, data from these will only be presented in listings, i.e. they will not contribute to any summary tables.

The sets of patients to be analysed are defined as follows:

- *all-patients-enrolled set* (APES) – all patients enrolled, including patients from study 16323A
- *all-patients-treated set* (APTS) – all patients from study 16159A who took at least one dose of Lu AF35700 in study 16159B
- *full-analysis set* (FAS) – all patients in the APTS (i.e. only patients from study 16159A are included) who had a valid baseline assessment and at least one valid post baseline assessment of PANSS total score in study 16159B.

Since this is an open-label study each patient will be classified according to these definitions based on information in data and no Classification Meeting will be held.

The classification will be done by the biostatistician.

The APTS will be used for presentations of safety data whereas the FAS will be used for presentation of efficacy data. Data listings will be based on the APES unless otherwise specified.

6 Descriptive Statistics

Unless otherwise specified, summary statistics (n, arithmetic mean, standard deviation [SD], median, lower and upper quartiles, minimum and maximum values) will be presented for continuous variables, and counts and, if relevant, percentages will be presented for categorical variables.

Summaries will be prepared overall and by the previous treatment (treatment group in study 16159A). To reflect the grouping of treatments in study 16159A, these will be grouped into the following categories (for 16159A patients only):

- Lu AF35700 10 mg
- Lu AF35700 20mg
- RIS/OLZ

Unless otherwise specified, data listings will include site, previous treatment group, patient screening number (from extension study), and lead-in study-Baseline information on sex, age, race, and weight. For the data listings, the previous treatment will be displayed as the specific treatment received in the lead-in study, i.e. it will belong to one of the categories Lu AF35700 10mg, Lu AF35700 20mg, Lu AF35700 30mg, Risperidone, Olanzapine, or Quetiapine.

7 Patient Disposition

7.1 Summary of Patient Disposition

Patient disposition in the treatment period will be summarised by previous treatment group and in total, as well as by country, and will include the number of patients in each analysis set

defined in chapter 5, and the number of patients in the APTS who completed or withdrew from treatment. The number of enrolment failures will also be displayed.

7.2 Withdrawals

The number of patients who withdrew from treatment will be summarized overall and by previous treatment both by primary reason for withdrawal, and all reasons for withdrawal.

Patients who withdrew from treatment will be listed and the listing will include the reason type (primary or secondary reason for withdrawal from treatment), the reason, specification of other reason, previous treatment group, date of Visit 2, date of withdrawal from treatment, and number of days on IMP in this study. Note that patients can have more than one secondary reason for withdrawal from treatment so the listing will include both the primary reason for withdrawal from treatment and all reasons for withdrawal from treatment.

Kaplan-Meier failure plots of time to withdrawal from treatment will be presented for the total group. The time will be calculated from the date of first dose of IMP in this extension study (for handling of missing IMP start date, see section 19.3.1) to the date of completion or withdrawal from treatment. Patients who completed treatment will be regarded as censored.

All tables and graphs will be based on the APTS. Listings will be based on the APES.

8 Demographics and Baseline Characteristics

Demographics (sex, age, age group, race, and ethnicity); baseline characteristics (height, weight, BMI, and waist circumference); baseline disease characteristics (age – and years since diagnosis of schizophrenia, years since first – and number of antipsychotic treatments, number of psychiatric hospitalizations), social histories; and baseline efficacy variables (PANSS total and subscale scores, CGI-S score, and PSP total score) will be summarized overall and by previous treatment group. CGI-S will be summarized both as a continuous and a categorical variable.

Concurrent as well as relevant past medical, neurological, and psychiatric disorders at the lead-in study Screening Visit will be coded using the *Medical Dictionary for Regulatory Activities* (MedDRA) and summarized.

A concurrent medical, neurological, or psychiatric disorder is a disorder that is ongoing at the Screening Visit of the lead-in study. A past medical, neurological, or psychiatric disorder is a disorder that ended prior to the Screening Visit of the lead-in study.

Demographics and baseline characteristics will be summarized based on the APTS, and baseline efficacy variables will be summarized based on the FAS.

9 Recent and Concomitant Medication

Recent and concomitant medication will be coded using the *WHO Drug Dictionary* (WHO-DDE).

Medications will be classified according to the start and stop time and summarized by anatomical therapeutic chemical (ATC) code levels 2 and 3, generic drug name, previous treatment group, and for each of the categories:

- Medication started before first dose of IMP (i.e. on-going concomitant medication from the lead-in study) and continued after first dose of IMP
- Concomitant medication started at or after first dose of IMP

The tables will be based on the APTS.

10 Exposure and Compliance

Exposure (days) to IMP in study 16159B will be calculated as:

$$\text{Last date of IMP} - \text{Start date of IMP} + 1$$

For details about handling of missing IMP start or stop date, see section 19.3.1 (IMP Start and Stop Dates).

The exposure for patients on the weekly dosing regimen will be summarized together with the exposure for patients on the daily dosing regimens.

Exposure to IMP will be summarized overall and by previous treatment group using descriptive statistics, and summaries will include the patient years of exposure (PYE). PYE will be calculated as the sum of the number of days of exposure to IMP for each patient, divided by 365.25 days.

In addition, exposure to IMP will be categorized in intervals 1 – 84 days [0 – 3 months], 85 – 168 days [3 – 6 months], 169 – 252 days [6 – 9 months], 253 – 336 days [9 – 12 months], > 336 days [>12 months], and summarized overall and by previous treatment group.

The final dose level for patients in APTS will be summarized overall and by previous treatment group.

The number of patients switching to the weekly dosing regimen will be summarized based on the APTS. The summary will include the number of patients going back to daily dosing after initiating weekly dosing.

Non-compliant days are days on which no IMP has been taken, less than the full dose of IMP has been taken, or more than the full dose of IMP has been taken.

Compliance (%) with IMP for the Treatment Period will be calculated as:

$$\frac{\text{Last date of IMP} - \text{Start date of IMP} + 1 - \text{Number of non-compliant days}}{\text{Last date of IMP} - \text{Start date of IMP} + 1} \times 100$$

where the number of non-compliant days is defined as the sum of all non-compliant days from the start of the interval to the end of the interval.

The compliance for patients on the weekly dosing regimen will be summarized together with the compliance for patients on the daily dosing regimens.

Compliance with IMP will be categorized as “≤80% compliant” or “>80% compliant”. The number and percentage of patients in each category will be summarised by previous treatment group and in total based on the APTS.

Exposure and compliance will be summarized based on the APTS.

11 Efficacy

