**Statistical Methodology**

- Safety and effectiveness assessments will be summarised descriptively.
- For *16159A-patients*, summaries will be prepared with respect to 2 baselines: Baseline 2 just prior to randomisation in study 16159A and Baseline in study 16159B. Summaries will be prepared overall and by the previous treatment (treatment group in the studies feeding into this extension study or previous treatment for patients not included in any Lu AF35700 study before).
- Specific tables of adverse events seen shortly after initiation of the weekly dosing regimen will be prepared.
- The statistical methodology will be detailed in a Statistical Analysis Plan.

[figure not shown]

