#### **17.7 Exposure and Compliance**

Exposure and compliance will be calculated per patient and summarised.

In particular, the amount of weekly dosing, frequency, duration, and reasons for initiation and termination, will be summarised.

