## 17.9 Safety Analyses

### 17.9.1 Analysis of Adverse Events

Adverse events will be classified according to the time of onset of the adverse event:

- *pre-study adverse event* – an adverse event that starts before the date of first dose of IMP in study 16159B.
- *Treatment-emergent adverse event (TEAE)* – an adverse event that starts or increases in intensity on or after the date of first dose of Lu AF35700 in study 16159B.

Adverse events, sorted by system organ class (SOC) and preferred term, will be summarised.

Specific tables of adverse events after weekly dosing will be prepared. Displays of all events while on weekly dosing, as well as events seen shortly after initiation of weekly dosing will be prepared.

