12.1.10 Adverse Events Leading to Dose Reduction

Adverse events leading to reduction of dose of Lu AF35700 in the Treatment Period will be listed.

Adverse events leading to reduction of dose of Lu AF35700 in the Treatment Period will be summarized by preferred term.

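### The SAP leaves out the protocol's summary of how long and why patients took weekly dosing, and its separate table of adverse events soon after the switch, and Section 18 does not list either omission

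*SAP*

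**What the plan says.** **Promised in the protocol.** Section 17.7 states: "In particular, the amount of weekly dosing, frequency, duration, and reasons for initiation and termination, will be summarised". The synopsis, under Statistical Methodology, states: "Specific tables of adverse events seen shortly after initiation of the weekly dosing regimen will be prepared". Section 17.9.1 promises two displays. One covers all events during weekly dosing, and the other is described by the words "as well as events seen shortly after initiation of weekly dosing will be prepared".

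**Kept in the SAP on exposure.** Section 10 defines a single exposure variable, running from first to last IMP date in the study, and states: "The exposure for patients on the weekly dosing regimen will be summarized together with the exposure for patients on the daily dosing regimens". Three items bear on weekly dosing:
- Switchers: "The number of patients switching to the weekly dosing regimen will be summarized based on the APTS"
- Returns: the same table also counts those who later revert to a daily regimen.
- Last dose: "The final dose level for patients in APTS will be summarized overall and by previous treatment group"

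**Kept in the SAP on adverse events.** Section 12.1.5 gives a listing of events during weekly dosing. Sections 12.1.6, 12.1.8 and 12.1.9 give tables of TEAEs, serious TEAEs and TEAEs leading to withdrawal during weekly dosing.

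**Declared as changed.** SAP 18 says that the separate daily-only displays will not be produced. It does not mention weekly duration, the reasons for switching, or the early post-switch display.

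**The concern.** SAP 1.2 keeps the exploratory objective of evaluating the long-term safety of both daily and weekly doses. Protocol 3.2 presents weekly dosing as a feasibility question for maintenance treatment. The SAP therefore plans three weekly adverse-event tables, but nothing that tells a reader how much weekly dosing lies behind them. A count of events could come from a few weeks of weekly treatment or from most of a year.

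The protocol also singled out the period just after the switch, and the SAP has no table confined to it. SAP 18 is where a reader looks for departures from the protocol, and that reader would not learn there that these summaries are gone.

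**Working it through.** The documents give no figure to reproduce: there is no sample size calculation, and no weekly duration is reported. The check is a comparison of promises with outputs, followed by a bound on what the planned tables can hide.

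**1. Promise against output**

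| Protocol item | SAP output |
|---|---|
| Extent and frequency of weekly dosing (17.7) | Partly kept: number switching, number returning, final dose level (Section 10) |
| Duration of weekly dosing (17.7) | None; the only exposure variable spans the whole study |
| Reasons for starting and stopping (17.7) | None |
| All events during weekly dosing (17.9.1) | Kept: listing and three tables (12.1.5, 12.1.6, 12.1.8, 12.1.9) |
| Events soon after weekly initiation (synopsis, 17.9.1) | No separate table |

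**2. Possible substitutes**
- SAP 12.1.10 states: "Adverse events leading to reduction of dose of Lu AF35700 in the Treatment Period will be summarized by preferred term". It is not split by regimen, and it cannot show why weekly dosing was started or why a patient returned to daily dosing for clinical worsening.
- The withdrawal-reason tables in SAP 7.2 concern leaving treatment, not changing regimen.
- The one early-window table in SAP 12.1.6 covers the two weeks after study entry, up to Day 14. Under Protocol 6.1 the earliest switch is the Week 8 visit (Day 56), and the first weekly tablet follows the last daily one by 7 days. At nominal visits that is Day 63, which is 63 − 14 = 49 days after the table closes. With the visit 6 days early, the gap is (56 − 6 + 7) − 14 = 43 days.
- The adverse-event listings (SAP 12.1.1) count days from the first IMP dose, not from the first weekly tablet.

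**3. What the exposure tables cannot distinguish**

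Inputs: a cap of 50 weekly patients (Protocol 6.1); the 7-day interval; visit days 56, 336 and 364 (Protocol Panel 2); and 365.25 days per patient-year (SAP 10). Assumptions: all 50 places are filled, everyone completes, no one returns to daily dosing, visits are nominal, and the last daily tablet is taken on the visit day.

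- All switch at Week 8: 364 − (56 + 7) = 301 weekly days each; 50 × 301 / 365.25 = 41.2 patient-years.
- All switch at Week 48: 364 − (336 + 7) = 21 weekly days each; 50 × 21 / 365.25 = 2.9 patient-years.
- Ratio: 301 / 21 = 14.3.

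In both cases the planned tables show 50 switchers, 0 returns, a final dose level of 70 mg/week for all 50, and pooled exposure of 50 × 364 / 365.25 = 49.8 patient-years. If 10 of the 50 had a given event, the crude rate would be 10 / 41.2 = 0.24 per patient-year in one case and 10 / 2.87 = 3.5 in the other.

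**4. Limit on attribution**

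Protocol 1.1.5.2 gives half-lives of 143 h (parent) and 250 h (metabolite). By simple half-life decay over the 7 days (168 h) before the first weekly tablet, 0.5^(168/143) = 0.44 of parent and 0.5^(168/250) = 0.63 of metabolite remain.

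**The case against.** The strongest reply is that little is lost. The switch and return counts, the listing and the three weekly event tables all survive. The extra ECGs around the switch (Protocol 9.5.5) are not assigned to visit windows, but SAP 12.5 brings all available assessments in the period into the evaluation of potentially clinically significant values. At most 50 of more than 500 patients are involved, and the study is descriptive. All of this stands, and it limits the severity.

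The 14-fold range is also a constructed extreme, since the documents give no actual weekly durations. That stands too. The range shows that duration cannot be recovered from the planned exposure tables, not how uneven it was in this trial.

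Three stronger readings are tempting, and the documents do not support them:
- **Early post-switch events go unreported.** An event starting after the first weekly tablet occurs during weekly dosing, so it enters the weekly TEAE table and listing, and the serious or withdrawal table where it qualifies. Only the separate time window is missing.
- **The pooling is concealed.** Section 10 states it openly, and an overall exposure summary is legitimate. The defect is an incomplete list of changes. The SAP 18 remark that all-patient tables suffice whatever the regimen is given as the reason for omitting the daily-only displays. It does not withdraw the promises in 17.7 and 17.9.1.
- **Weekly percentages will be diluted by the whole treated set.** The SAP states no denominator for these tables. The reference to the APTS may name only the source population, as it plausibly does for the by-sex table under the same heading.

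**Conclusion.** The point holds as a minor reporting gap between protocol and SAP. Three promised items are absent: weekly duration, the reasons for starting and stopping weekly dosing, and a table limited to the period soon after weekly initiation. SAP 18 does not declare their omission. The practical consequence is that the weekly adverse-event counts have no weekly time at risk beside them. Under the stated assumptions, the same exposure tables are compatible with anything from 2.9 to 41.2 patient-years of weekly dosing. That is an illustrative bound, not a forecast.

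The matter concerns an exploratory objective. The primary safety endpoints, reported overall, are unaffected.

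**What to change.** - **SAP 10:** add a summary of weekly exposure (number of patients, duration, patient-years) for patients with at least one weekly tablet.
- **SAP 12.1.6:** add a table of TEAEs starting within a stated window after the first weekly tablet. Neither document defines how soon counts as shortly after, so the SAP must set the window.
- **Reasons:** restore the summary of reasons for starting and stopping weekly dosing. If these were not captured, declare and justify the removal in SAP 18.

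Present the results descriptively. The investigator chose who switched, there are at most 50 such patients, and carry-over from daily dosing blurs attribution just after the switch, so the output should not be read as a comparison of weekly with daily dosing.

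The cost is some SAP wording and a few tables. The regimen dates are already needed to decide which events fall during weekly dosing. Whether reasons were recorded cannot be determined from the protocol and SAP.

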## 5.4 Withdrawal Criteria

A patient must be withdrawn from the study if:

- the patient and/or his or her legal representative (if applicable) withdraw(s) his or her consent (defined as a patient and/or his or her legal representative [if applicable] who explicitly take(s) back his or her consent); section 8.4 states how the patient's data will be handled
- the patient is lost to follow-up (defined as a patient who fails to comply with scheduled study visits or contact, who has not actively withdrawn from the study, and for whom no alternative contact information is available [this implies that at least two documented attempts have been made to contact the patient via both phone and mail]).

A patient must be withdrawn from treatment if:

- the investigator considers it, for safety, lack of efficacy, and/or study compliance reasons, in the best interests of the patient that he or she be withdrawn
- the patient becomes pregnant
- the patient has a serum ALT or AST value >3 times the upper limit of the reference range and a serum total bilirubin value >2 times the upper limit of the reference range
- the patient has a serum ALT or AST value >5 times the upper limit of the reference range that is confirmed by testing <2 weeks later
- the patient has a QTcF interval >500 ms or a change from Screening (or from Baseline for *16159A-patients* and *16323A-patients*) in the QTcF interval >60 ms concurrently with a QTcF interval >470 ms
- the patient has a positive urine drug screen verified by repeated testing at the following site visit
- the patient fails to comply with study procedures
- the patient is <80% IMP compliant between two consecutive, scheduled visits
- the patient in the opinion of the investigator has significant risk of suicide or who answers "Yes" to suicidal ideation questions 4 or 5 or answers "Yes" to suicidal behaviour on the C-SSRS® at any time during the study

Patients who withdraw will not be replaced.

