**For patients who completed study 16159A (*16159A-patients*)**

The Baseline Visit will take place at the same visit as the Visit 12 (Primary Outcome Visit, end of Week 16) of the study 16159A.

After the baseline assessment, for eligible patients, the treatment with Lu AF35700 will be initiated at daily dose of 10 mg at Day 1 of study 16159B. In addition, for *16159A-patients*, the treatment (Lu AF35700, risperidone or olanzapine) received during study 16159A will be tapered down in a blinded fashion with wallets from study 16159A and will be completed in 7 days according to the following scheme:

- Patients randomised to Risperidone: 4 mg/day for the first 3 days; 2 mg/day for the 4 subsequent days, encapsulated tablets, orally, once daily
- Patients randomised to Olanzapine: 10 mg/day for the first 3 days; 5 mg/day for the 4 subsequent days, encapsulated tablets, orally, once daily
- Patients randomised to Lu AF35700: Placebo for 7 days, encapsulated tablets, orally, once daily.

At the end of the first week (Week 1 Visit), all patients will be treated with 10 mg/day Lu AF35700 only.

From the Week 1 Visit, according to the investigator's clinical judgment, the 10 mg/day dose can be increased to 20 mg/day based on the patient's response. Thereafter, the 20 mg/day dose can be reduced to 10 mg/day based on the patient's tolerability to treatment. This can occur at scheduled or unscheduled visits.

From the Week 8 Visit, the switch from Lu AF35700 daily dosing regimen to Lu AF35700 weekly dosing regimen can be performed at any consecutive visit according to the investigator's clinical judgment. The first weekly tablet will be taken 7 days after the last daily tablet. The Lu AF35700 weekly dosing regimen can be switched back to a daily dosing regimen of 10 mg/day for tolerability reasons or to 20 mg/day for worsening of the patient's clinical status. This can occur at scheduled or unscheduled visits. The first daily tablet will be taken 7 days after the last weekly tablet.

The number of patients under weekly dosing regimen will be limited to 50 patients by IVRS/IWRS.

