	
 
- The switch from Lu AF35700 daily dosing regimen (10 or 20 mg/day) to Lu AF35700 weekly dosing regimen can be performed at the end of the eighth week (Week 8 Visit), according to the investigator's clinical judgment). First weekly tablet will be taken 7 days after the last daily tablet.
 
- No more than 50 patients can be assigned to weekly dosing regimen during the course of the study.
 
- Possibility to switch back to daily dosing regimen (for lack of tolerability or symptoms worsening). First daily tablet will be taken 7 days after the last weekly tablet.
 
					

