## **9.7 Treatment Compliance**

The responsible study personnel will dispense the IMPs. Accountability and compliance verification should be documented in the patient's source documents. Patients must be counselled on the importance of taking the study medications as directed at all study visits.

The medical monitor should be contacted if the investigator is uncertain whether a patient's lack of compliance warrants withdrawal from the study.

Patients must be counselled on the importance of taking the IMP as directed at all study visits.

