12.6.2 EPS Rating Scale Scores

For details about data handling, see section [19.1](#), [19.2](#).

Absolute and change from baseline in AIMS total score, mSAS total score, and BARS Global Clinical Assessment of Akathisia score (item 4) will be summarised at by week in the Treatment Period based on the APTS (baseline will also be included in the summaries of the absolute scores). The maximum change from baseline in the Treatment Period will also be summarised.

In addition, the BARS Global Clinical Assessment of Akathisia will be presented with descriptive tables showing number and percentage of patients in each category for baseline and by week in the Treatment Period based on the APTS.

The single-item scores for AIMS items 8 to 12 and BARS items 1 to 4 will be summarized by visit.

13 Pharmacokinetic/Pharmacodynamic Analyses

No pharmacokinetic/pharmacodynamics analyses are planned.

14 Blinded Data Reviews

Not applicable.

15 Interim Analyses

Not applicable.

16 Sample Size Considerations

No formal sample size calculation has been performed for the present study.

As stated in the clinical study protocol, it was expected that approximately 400 patients would be enrolled in the study distributed as follows: 270 from study 16159A, 30 from study 16323A and 100 patients who had not previously participated in a study investigating Lu AF35700. However, the distribution of the number of patients could be adjusted based upon the recruitment rate in each group. As mentioned in section 2, the actual patients recruited were for the most part from study 16159A except for 4 patients from study 16323A.

Since more than 500 patients are included in the study, it will be possible to obtain solid information on long-term safety of Lu AF35700.

To ensure sufficient exposure to the daily dosing regimen, the number of patients who completed study 16159A and who could be treated with the weekly dosing regimen was limited to 50 patients.

17 Statistical Software

The statistical software used will be SAS[®], Version 9.4 or later.

18 Changes to Analyses Specified in the Protocol

Due to the results from the lead-in study 16159A from which the majority of patients come from, the following changes have been made:

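### The SAP compliance rule counts planned tablet-free days on weekly dosing as non-compliant, so adherent weekly patients can fall in the ≤80% category

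*SAP*

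**What the plan says.** SAP section 10 (Exposure and Compliance) defines compliance as calendar days from first to last IMP, minus non-compliant days, divided by the same calendar days. On what is subtracted it says: "Non-compliant days are days on which no IMP has been taken, less than the full dose of IMP has been taken". Days above the full dose count as well. All such days are summed. Patients are then placed in two categories, ≤80% and >80%, by previous treatment group and in total.

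The only sentence there on how compliance is handled for weekly dosing is "The compliance for patients on the weekly dosing regimen will be summarized together with the compliance for patients on the daily dosing regimens". SAP sections 18 and 19 add no counting rule; 19.3.1 covers only missing IMP dates. Protocol 9.7 says "Accountability and compliance verification should be documented in the" patient's source documents, and does not say how days are counted.

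The weekly regimen is one 70 mg tablet per week, open to 16159A patients from the Week 8 Visit. Protocol 6.1 states: "The first weekly tablet will be taken 7 days after the last daily tablet". The same seven-day spacing applies on return to daily dosing. Protocol Panel 3 caps the regimen: "No more than 50 patients can be assigned to weekly dosing regimen during the course of the study".

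Protocol 5.4 also has an 80% limit among its reasons for withdrawal from treatment, "the patient is <80% IMP compliant between two consecutive, scheduled visits", again without defining compliance on weekly dosing.

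**The concern.** On weekly dosing, six days in every seven carry no tablet by design. A rule that treats any day without IMP as non-compliant therefore scores adherence to the regimen as non-adherence. The SAP clearly has weekly patients in view, since it sends them through the same calculation and the same 80% cut, but it provides no exception.

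At stake is the one compliance table planned. Protocol 3.2 names adherence as a possible benefit of weekly dosing, yet the table would tend to show these patients as the least compliant. Protocol 17.3 had promised separate displays for patients on daily dosing only, and SAP section 18 drops them, so no display would show that the low figures come from the regimen.

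**Working it through.** The plan states no compliance figure, so there is none to reproduce. I applied the SAP section 10 formula to a patient who takes every tablet.

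**Inputs.** First dose Day 1; nominal visit days and windows from Protocol Panel 2 (±6 days at Week 8, ±7 later, including the final visit); 52 weeks = 364 days; seven days between the last daily and the first weekly tablet (Protocol 6.1). Assumption: the last daily tablet is taken on the switch-visit day and the last weekly tablet on Day 364.

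**Rule as written.** With the last daily tablet on Day s and n weekly tablets on Days s+7, …, s+7n, IMP is taken on s+n days out of s+7n:

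score = (s+n)/(s+7n)

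| Switch visit | s | n | Score |
|---|---|---|---|
| Week 8 | 56 | 44 | 100/364 = 27.5% |
| Week 12 | 84 | 40 | 124/364 = 34.1% |
| Week 24 | 168 | 28 | 196/364 = 53.8% |
| Week 36 | 252 | 16 | 268/364 = 73.6% |
| Week 40 | 280 | 12 | 292/364 = 80.2% |
| Week 44 | 308 | 8 | 316/364 = 86.8% |

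**Visit windows.** Moving the switch and final visits to opposite ends of their windows gives:

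- Week 8: 95/365 = 26.0% to 104/356 = 29.2%
- Week 36: 263/371 = 70.9% to 273/357 = 76.5%
- Week 40: 287/371 = 77.4% to 297/357 = 83.2%
- Week 44: at least 311/371 = 83.8%

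Switches at Weeks 8 to 36 stay at ≤80%, Week 40 can fall on either side, and later switches stay above.

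**Where the cut falls.** 0.20 × 364 = 72.8, so a Day-364 completer needs 73 non-compliant days. Twelve intervals give 72 days (80.2%); thirteen give 78 (286/364 = 78.6%).

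**Patients who escape the cut.** A Week-8 switcher who stops at Day 70 scores 58/70 = 82.9%. One who returns to daily dosing after 11 weekly tablets has 12 intervals and scores (364 − 72)/364 = 80.2%.

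**Alternative reading: a missed scheduled tablet counts as one day.** A Week-8 switcher who misses 43 of 44 weekly tablets scores (364 − 43)/364 = 88.2% if the one taken is the last. If the one taken is the first, the interval ends there and the score is 100%. In general, missed weekly tablets number at most n while total days exceed 7n, so the loss is below 1/7 and the score stays above 6/7 = 85.7%.

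**Between-visit interval (Protocol 5.4).** Under the SAP rule, four weekly tablets taken on time over 28 days score 4/28 = 14.3%.

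**Share of the table.** SAP section 16 says "Since more than 500 patients are included in the study". With at least 501 patients, 50/501 = 10.0%; leaving out the four listing-only 16323A patients, 50/497 = 10.1%.

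**The case against.** The strongest reply is that nobody would program the rule literally. Full dose can be read relative to what was due. Protocol 5.4 also points that way: day-counting would put an adherent weekly patient at about 14% between visits, below that passage's limit, while Protocol 6.1 allows weekly dosing to continue. On this view the SAP merely omits a convention, and the percentages above are the consequence of one unlikely reading.

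The literal reading may well not be the intended one. But the SAP does not say what is intended, and its explicit words are that a day with no IMP is non-compliant. The obvious alternative within the same formula, one day per missed scheduled tablet, fails in the opposite direction, because missed weekly tablets can then never bring a patient to ≤80%. Reading the rule sensibly does not repair it.

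Other points stand and limit the finding. The table is descriptive, and no test, endpoint or analysis set depends on it. Adherence is neither an objective nor an endpoint. Protocol 17.7 says "In particular, the amount of weekly dosing, frequency, duration, and reasons for initiation and termination, will be summarised", but these are exposure items and do not promise a separate compliance figure, so a separate row for weekly patients is a preference. Protocol 5.4 is a site-level rule between visits, distinct from the SAP's whole-period summary; the link is only that both use 80% with compliance undefined for weekly dosing.

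**Conclusion.** The concern holds. As written, SAP section 10 classes fully adherent completers who switch at Weeks 8 to 36 and stay on weekly dosing as ≤80% compliant, with scores of 27.5% to 73.6% at nominal visit days. The classification survives the Protocol visit windows. It does not extend to all weekly patients: early stoppers, early returners to daily dosing and switches from Week 44 on can or do score above 80%, and Week 40 is borderline.

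The total-column percentage can shift by about 10 points at most, and by less in practice. A previous-treatment column could shift by more if weekly patients cluster in it, but column sizes are not given. The number of patients actually affected cannot be estimated from the documents. This should be corrected before the table is programmed; it does not threaten the primary safety results.

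**What to change.** In SAP section 10, state that on weekly dosing:

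- a tablet taken as scheduled makes its seven days compliant (the scheduled day and the next six, cut at the last IMP date);
- a missed tablet makes its seven days non-compliant;
- planned tablet-free days at a switch between regimens are compliant.

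The existing formula then works. The adherent Week-8 switcher scores 100%. With the last tablet taken, 10 of 44 missed gives 294/364 = 80.8%, 11 missed gives 287/364 = 78.8%, and 22 missed gives 210/364 = 57.7%, so the ≤80% category is reached from 11 missed tablets.

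Name the convention in the table footnote, and preferably show patients ever on weekly dosing in a separate row. Reconcile the use of compliance in Protocol 5.4 with the SAP definition.

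The cost is a short addition to SAP section 10, a footnote, one table row and the derivation code. No new data should be needed if the dosing records identify missed weekly tablets, which the documents do not describe. Seven-day coverage is itself a convention, late or extra weekly tablets would need a line in the derivation, and the separate row would hold at most 50 patients.
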